9.2. Setting

The study population will include US patients with SCD between the ages of 12 and 85 years who are enrolled in a health insurance plan (commercial, Medicare, Medicaid) continuously during the 365 days prior to and including the index date (baseline) and 180 days post-index. The index selection period is November 25, 2019 (date of Food and Drug Administration [FDA] accelerated approval for voxelotor) through January 31, 2023. The exposed group will include patients with a new prescription claim for voxelotor (no prior use 365 days prior to index date), while the control group will include matched patients who do not have a prescription claim for voxelotor. Non-voxelotor controls will include those receiving no SCD-modifying therapies as well as those receiving non-voxelotor SCD treatments to be reflective of clinical practice. Patients who have a history of stroke will be excluded from this analysis. Both the exposed and control groups may be treated with other SOC treatments such as HU and have 2 or more documented RBC transfusions prior to study index.

Depending on the source of information, approximately 50% of individuals with SCD in the US have received a RBC transfusion, and approximately 20% have received a transfusion in the past year. ¹⁶ In the feasibility assessment of Komodo Healthcare Map (KHM) dataset, race/ethnicity was documented for 90% (n=2230/2486) of patients with 87% (n=1929/2230) identifying as Black or African American. The Centers for Disease Control and Prevention (CDC) estimates 90% of individuals with SCD in the US are non-Hispanic Black or African American. ¹⁷ Socioeconomic status also plays an important factor in impacting patient behavior and access to care. While the KHM dataset does not have direct measures of patients' socioeconomic status, important indicators will be leveraged in the analysis for patients including geography by region, health insurance type, and whether a hematologist is involved in the patient's care. KHM is nationally representative of individuals with SCD. In the Komodo data, approximately 68% of patients have Medicaid as their primary insurance type.

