9.7.3. Outcome Analysis

Operational definitions for each outcome are described below. Each outcome will be assessed using the primary assessment method for the follow-up period where follow-up will end on the earliest of the following occurrences:

- Disenrollment from health insurance (with a 45-day allowable gap)
- Death
- Discontinuation of voxelotor (with a 45-day allowable treatment gap, voxelotor arm only)
- End of follow-up: up to 1 year from index date (365 days)
- The occurrence of any exclusion criteria events (e.g., pregnancy, stroke, hemodialysis, evidence of HSCT or gene therapy, renal transplant, or liver transplant)

The primary analyses will employ an as-treated follow-up approach that ends follow-up upon treatment changes. Patients will be followed from the index date until treatment change (discontinuation of voxelotor for voxelotor group), or the end of follow-up, whichever is earlier. This as-treated method of analysis allows for an estimate of the effect while the patient is taking the drug of interest and addresses intercurrent events. However, it may introduce bias into the estimates. To adjust for differences in follow-up time between voxelotor patients and their matched controls, matched or pairwise censoring will be applied to censor unexposed on the date of voxelotor discontinuation for their matched pair as a sensitivity analysis.³⁸ A summary of sensitivity analyses is included in Table 7 to evaluate how the magnitude of this bias will be assessed.

Primary Objective - Change in Number of RBC Transfusions PPPY

For each patient, the difference in the number of RBC transfusions PPPY from baseline to follow-up period will be reported as the change and will be calculated as follows:

$$Change = \left(\frac{Number\ of\ RBC\ transfusions\ in\ follow-up}{Available\ days\ of\ follow-up} - \frac{Number\ of\ RBC\ transfusions\ in\ baseline}{365\ days\ *}\right)x\ 365$$

The change in the number of RBC transfusions PPPY will be analyzed using generalized linear model (GLM) with an identity link to estimate the difference in RBC transfusion change rates between the two groups. If any pre-index covariates that are found to be unbalanced after the PS method, it will be included in the regression as a covariate. The rate change and its 95% confidence intervals (CI) will be reported.

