For sensitivity analysis, transformations of the outcome may also be considered as appropriate. The outcome data will only be viewed overall prior to selecting a method of regression. 95% CI will be reported for the difference between the groups. Full details will be provided in the SAP.

Exploratory Objective 1 – SCD-related Complications Exploratory Objective 1.1 – Change in SCD-related Complications PPPY

VOCs, ACS, ACS + pneumonia, and priapism will be assessed as the change in the rate of events PPPY from baseline to follow-up. For each individual, the rate of each clinical outcome will be calculated as the number of events divided by the number of person-days. The change will be calculated as:

$$Change = \left(\frac{Number\ of\ events\ in\ follow-up}{Available\ days\ of\ follow-up} - \frac{Number\ of\ events\ in\ baseline}{365\ days\ *}\right)x\ 365$$
*All patients have 365 days of baseline data

The change in number of events PPPY will be analyzed using GLM with an identity link to estimate the difference in clinical outcome change rates between the two groups. If any preindex covariates that are found to be unbalanced after the PS method, it will be included in the regression as a covariate. The rate change and its 95% CI will be reported.

Exploratory Objective 1.2 – Time to Stroke

Stroke will be assessed as a time-to-event outcome. Cox proportional hazards (PH) models will be used to calculate the hazard ratio (HR); 95% CIs will be calculated using a robust variance estimator.

Exploratory Objective 2, Endpoint 1 – Number of RBC Transfusions PPPY in Follow-Up

The number of RBC transfusions that occur during the follow-up period will be assessed PPPY during available follow-up within each group. The mean number of RBC transfusions PPPY will be reported for each group. The mean difference between the groups will be assessed using a GLM similar to the primary analysis. The 95% CI will be reported for the difference between the groups.

Exploratory Objective 2, Endpoint 2 – Proportion of Patients with > 30% Reduction in RBC Transfusions

^{*}All patients have 365 days of baseline data

This outcome will be defined as the proportion of patients with a percent reduction in RBC transfusions between baseline and follow-up that is greater than 30%. For each patient, the percent change will be calculated as follows:

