Subgroup analysis by concomitant medications	A subgroup analysis will be performed on patients who received hydroxyurea, crizanlizumab, L-glutamine, and/or ESA in baseline the exposed and referent groups. This subgroup analysis will be performed for the Primary Objective and the Exploratory Objective 1 (VOCs).	To understand the effect of other SCD treatments.

Abbreviations: ITT: Intention-to-treat; PPPY: per patient per year; SCD: Sickle cell disease

All subgroup analyses and stratifications must meet a minimum sample size criteria in each group to be performed (see SAP for more detail). Exploratory objective 1 which evaluates the change in the rate of VOCs and its separate components from baseline through follow-up will also include a sensitivity analysis utilizing alternative definitions for VOCs, given a higher likelihood of misclassification in claims using ICD-10 codes alone; these alternative VOC definitions will be detailed in code lists provided in the SAP. Other sensitivity analyses such as e-values may be considered if other possible confounders or sources of bias are identified, depending on effect size in the primary outcome or differences in baseline characteristics and/or follow-up time between the exposed and matched controls. Details on potential sensitivity analyses will be included in the SAP.

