	Definition 2 (sensitivity analysis, broad definition): • Presence of ICD-10 diagnoses code for VOCs (definition 1) and/or VOC component (e.g., ACS, priapism, stroke, splenic sequestration, or crisis unspecified) on a claim from one of the following healthcare settings:	

V2.0 23 December 2024	T s	
	 Telemedicine visit Office clinic visit: Outpatient visit Urgent care visit Emergency visit Inpatient visit 	
	Final definition to be included in SAP.	
Venous Thromboembolism	Presence of an ICD-10-CM diagnosis code on any claim	
Avascular Necrosis	Presence of an ICD-10-CM diagnosis code on any claim	
Cholelithiasis	Presence of an ICD-10-CM diagnosis code on any claim	
Chronic Kidney Disease	Presence of an ICD-10-CM diagnosis code on any claim	
Chronic Pain	Presence of an ICD-10-CM diagnosis code on any claim	
Diabetes	Presence of an ICD-10-CM diagnosis code on any claim	
Heart Failure	Presence of an ICD-10-CM diagnosis code on any claim	
Iron Overload	Presence of an ICD-10-CM diagnosis code on any claim	
Leg Ulcer	Presence of an ICD-10-CM diagnosis code on any claim	
Pulmonary Hypertension	Presence of an ICD-10-CM diagnosis code on any claim	
Retinopathy	Presence of an ICD-10-CM diagnosis code on any claim	
Treatments		
Voxelotor	Presence of a national drug code (NDC) or generic name on a pharmacy event claim	

7	12	0	23	D	ecem	her	20	24

1 - 1 - 1 - 1 - 1 - 1 - 1 - 1 - 1 - 1 -	
Hydroxyurea	Presence of a national drug code (NDC) or generic name on a pharmacy event claim
Crizanlizumab	Presence of a national drug code (NDC) or generic name on a pharmacy event claim
	OR
	Presence of an ICD-10-CM procedure, Current Procedural Terminology (CPT), or Healthcare Common Procedure Coding System (HCPCS) code on any claim
L-glutamine	Presence of a national drug code (NDC) or generic name on a pharmacy event claim
Erythropoietin Stimulating Agent	Presence of a national drug code (NDC) or generic name on a pharmacy event claim
(ESA)	OR
	Presence of an ICD-10-CM procedure, Current Procedural Terminology (CPT), or Healthcare Common Procedure Coding System (HCPCS) code on any claim
Other Covariates	
RBC transfusion	Presence of an ICD-10-CM procedure, Current Procedural Terminology (CPT), or Healthcare Common Procedure Coding System (HCPCS) code on any claim
	Multiple codes or claims occurring on the same day will be assessed as a single RBC transfusion event.
Hb lab test	Presence of a LOINC or CPT/HCPCS code,
	OR no presence of a LOINC or CPT/HCPCS code

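### The broad VOC definition counts stroke, which is excluded at baseline and ends follow-up, so in the change score a stroke can only add, over a denominator that it shortens itself

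*Protocol*

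**What the plan says.** Four parts of the protocol meet here.

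- **Definition.** Annex Table 1 defines VOC twice. Definition 1, the strict one used in the main VOC analysis, lists VOC and dactylitis codes and no stroke. Definition 2, the broad one for sensitivity analysis, adds any "VOC component (e.g., ACS, priapism, stroke, splenic sequestration, or crisis unspecified) on a claim from one of the following healthcare settings". The entry closes with "Final definition to be included in SAP".
- **Baseline.** Section 9.2 states: "Patients who have a history of stroke will be excluded from this analysis". Table 3 makes this operational as at least one claim with a stroke diagnosis in the baseline year.
- **Follow-up.** Section 9.7.3 lists the events that end follow-up for each outcome, among them "The occurrence of any exclusion criteria events (e.g., pregnancy, stroke, hemodialysis, evidence of HSCT or gene therapy, renal transplant, or liver transplant". Footnote 4 of Figure 1 says the same. Otherwise the limit is "End of follow-up: up to 1 year from index date (365 days".
- **Endpoint.** For Exploratory Objective 1.1, "VOCs, ACS, ACS + pneumonia, and priapism will be assessed as the change in the rate of events PPPY from baseline to follow-up", and "the rate of each clinical outcome will be calculated as the number of events divided by the number of person-days". The displayed formula subtracts baseline events over 365 days and multiplies by 365. The model is a GLM with identity link.

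Table 5 adds that VOC events must be more than 5 days apart to count separately. Stroke also has its own time-to-event analysis, Exploratory Objective 1.2.

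**The concern.** A change score compares like with like only if an event can be counted in both periods. Under Definition 2 a stroke cannot: its baseline count is zero because of how the cohort is selected. It also ends the patient's observation, so it sets the denominator over which it is annualised. ACS, priapism, splenic sequestration and unspecified crisis have neither property, because none of them is an exclusion or a censoring event.

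The protocol has already applied this reasoning elsewhere. The version 1.1 entry in Section 5 explains that stroke was taken out of the baseline comorbidity list because, as an exclusion, it would not be measured at baseline. Definition 2 did not follow.

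Definition 2 exists to test whether the VOC result survives misclassification in claims (Sections 9.7.3 and 9.9). If one or two early strokes separate the two definitions, the reader may take this for a misclassification effect when it is an artefact of the scale.

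**Working it through.** The protocol states no figure for VOC or stroke, so there is none to reproduce.

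**1. Contribution of one stroke.** Let a stroke on day t be counted, end follow-up that day, and lie more than 5 days from any other counted event. Its contribution to the change score is (1/t − 0/365) × 365 = 365/t. This assumes that Definition 2 uses the same stroke codes as the exclusion.

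| Day t | 10 | 30 | 180 | 365 |
|---|---|---|---|---|
| 365/t | 36.5 | 12.2 | 2.0 | 1.0 |

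Under Definition 1 a stroke also shortens the denominator, but it adds nothing to the numerator. The 365/t term is therefore specific to Definition 2.

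**2. Dependence on timing (assumed; the protocol gives none).** Stroke day is taken as uniform from a first day to day 365.

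| First possible day | Mean of 365/t | Median | Maximum | Mean of (365/t)² |
|---|---|---|---|---|
| 1 | 6.48 | 1.99 | 365 | 599.4 |
| 7 | 4.10 | 1.96 | 52.1 | 56.0 |
| 30 | 2.73 | 1.85 | 12.2 | 12.4 |
| 90 | 1.86 | 1.60 | 4.1 | 4.07 |
| 180 | 1.40 | 1.34 | 2.03 | 2.03 |

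With a start at day 1, only 15% of strokes score above 6.5. The mean and mean square come from the first days.

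**3. Effect on an arm.** For an assumed one-year stroke risk p, the added mean is p × E[365/t]. The added variance is p × E[(365/t)²] − (p × E[365/t])². With uniform timing from day 1:

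| p | 0.1% | 0.5% | 1% | 2% | 5% |
|---|---|---|---|---|---|
| Added mean (PPPY) | 0.006 | 0.03 | 0.06 | 0.13 | 0.32 |
| SD contribution | 0.77 | 1.73 | 2.45 | 3.46 | 5.46 |

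**4. Effect on the total SD.** At p = 1% the added variance is 0.01 × 599.4 − 0.0648² = 5.99. The protocol gives no VOC SD, so three values are assumed:

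- SD 3: √(9 + 5.99) = 3.87
- SD 5: √(25 + 5.99) = 5.57
- SD 8: √(64 + 5.99) = 8.37

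The 3.0 in Section 9.5 is for transfusion change and serves only as one of these values. If strokes start at day 7, the added variance is 0.01 × 55.97 − 0.041² = 0.56 and SD 3 becomes only √9.56 = 3.09. Most of the inflation therefore comes from the first six days.

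**5. Effect on the group difference.** Stroke risks of 1% and 2% move the difference by 0.01 × 6.48 = 0.065 PPPY, or by 0.01 × 1.40 = 0.014 if no stroke comes before day 180. Equal risk and timing give zero. For scale, at the primary endpoint's 185 and 370 patients and SD 3, the standard error before any propensity-score inflation is √(9 × (1/185 + 1/370)) = 0.27.

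**6. Effect of one actual event.** In the voxelotor arm, one stroke on day 10 moves the arm mean by 36.5/185 = 0.20, on day 30 by 12.2/185 = 0.07, and on day 180 by 2.0/185 = 0.01. In the control arm the shifts are half as large.

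**The case against.** **The definition is not final.** The protocol says so in the same cell and adds that "these alternative VOC definitions will be detailed in code lists provided in the SAP". The component list is given as examples, and the SAP is not shown. This limits the weight of the point but does not answer it. Stroke is named, and a code list built from this text would include it. Deferral means the correction can still be made at no cost.

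**The 180-day rules in Table 2 protect the denominator.** They do so only in part. They require 180 days of enrollment in both arms, and 180 days of voxelotor use in the exposed arm. They do not require 180 stroke-free days. They would probably remove some early strokes, so uniform timing from day 1 is a harsh assumption. They also act unequally: a voxelotor patient who stops the drug after an early stroke leaves the cohort, while a comparable control stays. As a bound, assume equal 1% risk, uniform timing, and that every exposed patient with a stroke before day 180 is lost. Controls then gain 0.01 × 6.48 = 0.065 PPPY and the voxelotor arm 0.01 × (186/365) × 1.40 = 0.007. The gap of about 0.06 would favour voxelotor. It is small against a standard error of 0.27.

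**The variability may be much larger than 3.** Definition 2 also takes in office, outpatient and telemedicine claims. At SD 8 the rise is about 5%. This stands.

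**The 5-day rule can absorb a stroke.** This also stands: a stroke code close to another counted crisis adds no separate event, so 365/t is an upper value.

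**Reach is small.** External hematologists advised on how to capture VOCs in claims, the analysis is exploratory, and Definition 1 does not list stroke. All true. Clinical advice that stroke belongs among sickle cell complications would still not make it measurable as a change from a baseline where it cannot occur.

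**Conclusion.** The structural flaw holds on the protocol's own text. Under Definition 2 a stroke can only raise the change score, and it is annualised over a follow-up that it ends itself. Stroke is the only listed component with this property.

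The size is open. It depends on stroke incidence, stroke timing and VOC variability, none of which is stated. A reader might infer that each stroke counts as about six and a half events and that strokes would dominate the sensitivity analysis. The documents do not support that. The 6.5 is a mean under uniform timing from day 1, driven by the first days. The median is about 2, and the mean falls to 1.4 if no stroke comes before day 180. The shift in the group difference is 0.065 PPPY per percentage point of risk difference, about a quarter of a standard error of 0.27. It cancels when risk and timing are equal.

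What remains is the chance that a few early strokes add noise, or a disagreement with Definition 1 that has nothing to do with claims misclassification. Severity is minor: a provisional sensitivity definition of an exploratory endpoint. The primary objective and the main VOC analysis do not use it.

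**What to change.** Remove stroke from the example components of VOC Definition 2 in Annex Table 1, and from the matching SAP code list when the definition is finalised. Keep ACS, priapism, splenic sequestration and unspecified crisis, which can be counted in both periods and do not end follow-up. Leave stroke to Exploratory Objective 1.2, where ending follow-up at the event is the natural design.

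The cost is one word in the protocol and one block of codes. Sample size, cohort and other endpoints are unaffected, and no information on stroke is lost.

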Population: The study population will include individuals with SCD between 12 and 85 years of age who are enrolled in a health insurance plan (commercial, Medicare, Medicaid) continuously during the 365 days prior to and including the index date (baseline) and 180 days post-index. The index selection period will be November 25, 2019 (date of FDA accelerated approval for voxelotor) through January 31, 2023. The exposed group will include patients with a new prescription claim for voxelotor (no use 365 days prior), while the control group will include matched patients who do not have a prescription claim for voxelotor. The exposed group will index on the voxelotor prescription claim date and will be sequentially coarsened-exact-matched with up to four non-voxelotor patients based on age and calendar date. Both the exposed and control groups may be treated with other standard of care (SOC) treatments, such as hydroxyurea, during the study period.

Variables: The exposure of interest will be a voxelotor prescription claim. Baseline characteristics and covariates for PS modeling will include demographic information (e.g., age, sex, insurance type) as well as patient characteristics (e.g., specialty provider type, common SCD comorbidities, treatment history, Hb levels, number of prior RBC transfusions, and healthcare utilization). The primary outcome of interest is RBC transfusion. Exploratory outcomes include VOC, stroke, and RBC transfusion complications. Tables 4 and 5 define exposures, outcomes, and key covariates.

Data sources: The study will use the Komodo Healthcare Map (KHM) database linked to Claritas prescription data (proprietary voxelotor claims) and Quest Diagnostics lab data. Data sources are anchored on a closed system of administrative claims, including patient enrollment, physician, facility, and pharmacy claims.

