An important non-pharmacologic intervention for SCD is RBC transfusion.³ RBC transfusions are indicated for severe symptomatic anemia, acute complications like stroke or acute multi-organ failure, and/or secondary prevention of stroke or recurrent pain crises in individuals with SCD.³ The two primary types of RBC transfusions, simple (addition of RBCs without removal of the patient's blood) and exchange (removal of the patient's blood and replacement with donor packed RBCs), have both acute and chronic indications. Treatment guidelines recommend acute transfusions for symptomatic anemia, ACS, multiorgan failure, and preoperatively; chronic transfusions, usually administered monthly,

are recommended for stroke prevention.³ While blood transfusions can improve SCD complications, they are also associated with important risks that can occur at each transfusion: resultant iron overload can lead to end organ damage, alloimmunization can lead to delayed hemolytic transfusion reactions (DHTR) and mortality, and transfusion transmitted infections can cause organ damage and mortality.^{3,8–11} Additionally, transfusion administration can be burdensome to patients due to the need for frequent venous access, which can cause pain, psychological distress, and interruptions to daily life.¹² A significant unmet need exists for new therapies and interventions that address the clinical complications of SCD while mitigating the patient burden.

Once-daily oral administration of voxelotor has been shown to reduce red-cell sickling, blood viscosity and improve red-cell deformability in vitro and to extend red-cell half-life and reduce anemia and hemolysis in vivo. ¹³ Evidence from clinical studies has demonstrated that voxelotor has a beneficial effect on Hb levels, a critical factor in the decision for an RBC transfusion. However, no clinical trials have demonstrated the impact of voxelotor on rates of RBC transfusion. While preliminary real-world evidence (RWE) supports a reduction in RBC transfusions associated with voxelotor use, these studies are limited by small sample sizes and lack of comparator populations. ^{14,15}

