Table 5. Description of Endpoints and Alignment to Study Objectives

Endpoint	Assessment Period	Output	Objective Alignment
Change in RBC transfusions	[Baseline]; [Follow-up]	Mean change in the number of RBC transfusions (maximum 1 per day) PPPY from baseline to follow-up	Primary Objective
VOCs	[Baseline]; [Follow-up]	Mean change in the number of events (maximum 1 per day) PPPY from baseline to follow-up. VOC events need to occur more than 5 days apart to be considered separate events.	Exploratory Objective 1.1
ACS	[Baseline]; [Follow-up]	Mean change in the number of events (maximum 1 per day) PPPY from baseline to follow-up	Exploratory Objective 1.1
ACS Including Pneumonia	[Baseline]; [Follow-up]	Mean change in the number of events (maximum 1 per day) PPPY from baseline to follow-up	Exploratory Objective 1.1
Priapism	[Baseline]; [Follow-up]	Mean change in the number of events (maximum 1 per day) PPPY from baseline to follow-up	Exploratory Objective 1.1

Voxelotor

V2.0 23 December 2024		9	
Stroke (including transient ischemic attack)	[Follow-up]	Time to event during follow-up	Exploratory Objective 1.2
RBC transfusions in follow-up	[Follow-up]	Mean number of RBC transfusions (maximum 1 per day) PPPY in follow-up	Exploratory Objective 2
Percent reduction in RBC transfusion > 30%	[Baseline]; [Follow-up]	Proportion of patients with a percentage decrease in the number of RBC transfusions (maximum 1 per day) PPPY from baseline to follow-up that is greater than 30%	Exploratory Objective 2
Zero RBC transfusions in follow-up	[Follow-up]	Proportion of patients with 0 RBC transfusions (maximum 1 per day) PPPY during follow- up	Exploratory Objective 2
Iron overload	[Follow-up]	Time to event during follow-up	Exploratory Objective 3
Iron chelation use	[Follow-up]	Time to event during follow-up	Exploratory Objective 3
Delayed hemolytic transfusion reactions	[Follow-up]	Time to event during follow-up	Exploratory Objective 3
Alloimmunization	[Follow-up]	Time to event during follow-up	Exploratory Objective 3
Composite outcome (iron overload, iron chelation use, delayed hemolytic transfusion reactions, and/or alloimmunization)	[Follow-up]	Time to event during follow-up	Exploratory Objective 3

Abbreviations: ACS: Acute Chest Syndrome; PPPY: per patient per year; RBC: Red blood cell; VOC: vaso-occlusive crisis The table above includes a summary of the outcomes of interest for this analysis. Operational definitions can be found in the data analysis plan (Section 9.7).

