Annex Table 2. RBC Transfusion Codes

Code	Description	Code Type
3643 0	Transfusion, blood or blood components	CPT

Mark Committee of the C	December 2024	
3644 0	Push transfusion, blood, 2 years or under	CPT
3645 0	Exchange transfusion, blood, newborn	CPT
3645 5	Exchange transfusion, blood; other than newborn	CPT
3645 5	EXCHNG TRANSFUSION BLOOD OTHER/THAN NEW BORN	CPT
3651 6	Therapeutic apheresis; with extracorporeal immunoadsorption, selective adsorption, or selective filtration and plasma reinfusion	CPT
P901 0	BLOOD (WHOLE), FOR TRANSFUSION, PER UNIT	HCPC S
P901 1	BLOOD, SPLIT UNIT	HCPC S
P901 6	Red blood cells, leukocytes reduced, each unit	HCPC S
P902 1	Red blood cells, each unit	HCPC S
P902 2	Red blood cells, washed, each unit	HCPC S
P903 8	Red blood cells, irradiated, each unit	HCPC S
P903 9	Red blood cells, deglycerolized, each unit	HCPC S
P904 0	Red blood cells, leukocytes reduced, irradiated, each unit	HCPC S
P905 1	Whole blood or red blood cells, leukocytes reduced, cmv-negative, each unit	HCPC S
P905 4	Whole blood or red blood cells, leukocytes reduced, frozen, deglycerol, washed, each unit	HCPC S
P905 7	Red blood cells, frozen/deglycerolized/washed, leukocytes reduced, irradiated, each unit	HCPC S
P905 8	Red blood cells, leukocytes reduced, cmv-negative, irradiated, each unit	HCPC S
3023 0N1	Transfusion of Nonautologous Red Blood Cells into Peripheral Vein, Open Approach	ICD10 PROC

V 2.0 23 1	December 2024	
3023	Transfusion of Nonautologous Frozen Red Cells into Peripheral Vein, Open	ICD10
0P1	Approach	PROC
3023	Transfusion of Nonautologous Red Blood Cells into Peripheral Vein,	ICD10
3N1	Percutaneous Approach	PROC
3023	Transfusion of Nonautologous Frozen Red Cells into Peripheral Vein,	ICD10
3P1	Percutaneous Approach	PROC
3024	Transfusion of Nonautologous Red Blood Cells into Central Vein, Open	ICD10
0N1	Approach	PROC
3024	Transfusion of Nonautologous Frozen Red Cells into Central Vein, Open	ICD10
0P1	Approach	PROC
3024 3N1	Transfusion of Nonautologous Red Blood Cells into Central Vein, Percutaneous Approach	ICD10 PROC
3024	Transfusion of Nonautologous Frozen Red Cells into Central Vein,	ICD10
3P1	Percutaneous Approach	PROC
3025	Transfusion of Nonautologous Red Blood Cells into Peripheral Artery, Open	ICD10
0N1	Approach	PROC
3025	Transfusion of Nonautologous Frozen Red Cells into Peripheral Artery, Open	ICD10
0P1	Approach	PROC
3025	Transfusion of Nonautologous Red Blood Cells into Peripheral Artery,	ICD10
3N1	Percutaneous Approach	PROC

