3025	Transfusion of Nonautologous Frozen Red Cells into Peripheral Artery,	ICD10
3P1	Percutaneous Approach	PROC
3026	Transfusion of Nonautologous Red Blood Cells into Central Artery, Open	ICD10
0N1	Approach	PROC
3026	Transfusion of Nonautologous Frozen Red Cells into Central Artery, Open	ICD10
0P1	Approach	PROC
3026	Transfusion of Nonautologous Red Blood Cells into Central Artery,	ICD10
3N1	Percutaneous Approach	PROC
3026	Transfusion of Nonautologous Frozen Red Cells into Central Artery,	ICD10
3P1	Percutaneous Approach	PROC
6A55 0Z0	Pheresis of Erythrocytes, Single	ICD10 PROC
6A55 1Z0	Pheresis of Erythrocytes, Multiple	ICD10 PROC

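### Baseline transfusion history is balanced only as a count of days, although exchange and erythrocyte-pheresis codes already in the code list give a partial marker of modality

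*Protocol*

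**What the plan says.** Section 7 of the protocol names two modalities: "The two primary types of RBC transfusions, simple (addition of RBCs without removal of the patient's blood) and exchange". It adds that each is used both acutely and chronically, and that chronic transfusion is usually monthly.

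Annex Table 2 puts all qualifying codes in one list. Among them are a general code, "Transfusion, blood or blood components" (CPT 36430), an exchange code, "Exchange transfusion, blood; other than newborn" (CPT 36455), and two red-cell apheresis codes, 6A550Z0 ("Pheresis of Erythrocytes, Single") and 6A551Z0. The rest are mainly blood-product codes and ICD-10-PCS transfusion codes defined by vessel and approach.

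Annex Table 1 gives the same-day rule: "Multiple codes or claims occurring on the same day will be assessed as a single RBC transfusion event". Table 5 builds the primary endpoint on the pooled count: "Mean change in the number of RBC transfusions (maximum 1 per day) PPPY from baseline to follow-up".

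For confounding control, the Abstract lists "number of prior RBC transfusions, and healthcare utilization" among the propensity-score covariates, and Table 4 has one transfusion row, a continuous variable. No row of Table 4 records modality. Table 7 stratifies by the baseline number of transfusions and has no subgroup by modality. The limitations in Section 9.9 discuss units of blood and several claims on one day, but not exchange versus simple transfusion. Section 9.4 says that the sponsor's validation study set out to record the type of transfusion; no variable in this protocol uses it.

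**The concern.** The primary endpoint is change from a baseline year in which every patient had at least 2 transfusions. Patients selected on a high count caused by acute events can be expected to fall back somewhat without any drug. Patients on a standing programme have less reason to. Two patients with the same baseline count can therefore have different expected changes if untreated. If voxelotor was started more often, or less often, in one of these groups, the arms would differ in change with no drug effect, even with the count well balanced.

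The protocol treats this as a validity issue. Table 3 excludes stroke, hemodialysis and transplant history because such patients may depend on transfusion. Section 9.9 gives the stroke exclusion the purpose of removing patients transfused chronically for secondary prevention. It then says that patients transfused for primary stroke prevention cannot be identified, and calls them few on the basis of a figure of under 5% of pediatric patients with the disease. That figure does not describe a cohort aged 12 to 85 selected for at least 2 transfusions in a year. A partial marker of planned transfusion is present in the protocol's own code list, and neither the propensity score nor the balance check uses it.

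**Working it through.** **1. What the codes can show.** An exchange or erythrocyte-pheresis code marks an exchange procedure. The general code, the blood-product codes and the ICD-10-PCS transfusion codes can accompany either modality. The list therefore supports a flag for any exchange or erythrocyte-pheresis code in baseline. It supports simple transfusion only by absence of such a code.

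**2. What the balance check covers.** Table 6 requires an ASD of at most 0.10 for the covariates. The transfusion covariate in Table 4 is a count, so the check bears on the count and on the proxies, and on modality only as far as these predict it.

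**3. The plan's precision (Section 9.5).** Inputs: SD 3.0, difference 1, ratio 1:2, factor 1.65, 80% power. Two-sided alpha of 0.05 is assumed, in line with the 95% intervals.
- Treated patients before inflation: (1 + 1/2) × [3.0 × (1.960 + 0.842)]² = 105.96, rounded up to 106.
- After inflation: 106 × 1.65 = 174.9, so 175 treated and 350 controls.
- The plan states 185 and 370, which gives power of 82.2%. It is slightly conservative, and the point here does not depend on it.
- Standard error at 185/370: 3.0 × √1.65 × √(1/185 + 1/370) = 0.347.

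**4. Illustrative bias.** The protocol gives no modality shares and no untreated change by modality, so both inputs are assumptions.

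Bias = (residual difference between arms in exchange share) × (difference between modalities in untreated change per patient per year).

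Rejection rate with no drug effect = 1 − Φ(1.96 − bias/0.347) + Φ(−1.96 − bias/0.347).

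- 0.05 × 1 = 0.05: rejection rate 0.052
- 0.10 × 1 = 0.10: 0.060
- 0.10 × 2 = 0.20: 0.089
- 0.20 × 2 = 0.40: 0.211
- 0.20 × 3 = 0.60: 0.409

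The low end is 0.05/0.347 = 0.14 of a standard error. The high end is 0.60/0.347 = 1.73 standard errors.

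**5. What checking the flag would achieve.** For a binary variable, ASD = gap / √(mean of the two arms' p(1 − p)). The root is at most 0.5, so ASD ≤ 0.10 implies a gap of at most 0.10 × 0.5 = 0.05. Under the same assumed differences of 1 to 3, the bias carried by the flag is then at most 0.05 to 0.15. Modality that the codes miss is not covered by this bound.

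**The case against.** Four objections deserve an answer.

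*Modality is not indication.* Section 7 gives both types acute and chronic uses. What would drive a different untreated course is planned versus episodic transfusion, and an exchange flag does not measure that directly. This stands. The flag is an imperfect marker, and the protocol does not say that exchange patients are the ones who fail to fall back.

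*The codes do not separate the modalities cleanly.* This also stands. It limits the adjustment but does not prevent the flag from being derived.

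*The plan already deals with much of this.* Baseline stroke is excluded. The count itself carries information on monthly programmes, and the primary result is reported by categories of it. Iron overload, chelation, hematology provider, visits and complications are candidate covariates. Section 9.9 admits unmeasured confounding, and Section 9.7.3 allows e-values. These measures reduce the residual gap, and so make the upper end of the range above doubtful. They are proxies, however, and leave a variable obtainable from the code list unchecked.

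*The covariate list is only provisional.* Table 4 describes possible covariates, and the statistical analysis plan, which is not shown, could add one. But the protocol itself fixes the endpoint, the transfusion codes and the candidate list, and Section 9.7.2 presents the propensity-score list as set in advance and comprehensive.

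A reader might infer that the arms do differ in modality, that exchange means planned and simple means acute, or that the planned diagnostics are blind to the problem. The documents support none of these: they contain no modality data by arm, they give both types both kinds of use, and the proxies would pick up part of any imbalance.

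**Conclusion.** The point holds as a gap in confounding control, not as a demonstrated bias. Balance on the number of transfusion days does not establish balance on modality, and the protocol leaves unused a partial marker that its own code list provides. Size and direction are unknown, so a drug effect could be mimicked or masked. The illustrative 0.05 to 0.60 transfusions per patient per year, against the design difference of 1, rests wholly on the assumed gaps of 5 to 20 points and differences of 1 to 3. The lower part of that range is the more plausible after matching on the count and the proxies. The change should be made because it is cheap and bears on the primary endpoint; nothing shows that the analysis fails without it.

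**What to change.** Derive from Annex Table 2 a baseline variable for any exchange or erythrocyte-pheresis code (36455, 6A550Z0, 6A551Z0), and the number of such days. Add it to Table 4 as a baseline characteristic and propensity-score covariate. Report its ASD before and after matching under Table 6, and carry it into the outcome model if it remains imbalanced. Add to Table 7 a supportive report of the primary result by this flag, subject to the minimum subgroup size. State in Section 9.9 that modality is only partly captured.

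The cost is one or two derived variables from codes already listed, with no new data and no change in sample size. Section 9.7.2 has the propensity-score work done blind to outcomes, so the change belongs in that phase. The drawback is that some exchanges will carry no exchange code, so the unflagged group will be mixed and the adjustment partial. If the flag is rare in either arm, the protocol's positivity and model-fit rules may keep it out of the propensity score; its distribution by arm should still be reported.
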